8.2. Safety Assessments

All safety assessments will be performed at the times outlined in the Schedule of Activities (Section 1.2). Additional (unscheduled) safety assessments may be performed as needed.

8.2.1. Medical and Surgical History

Medical and surgical history will be obtained at the Screening Visit. Medical history will include a review of the following systems: general, dermatological, respiratory, cardiovascular, gastrointestinal, genitourinary, gynecological, endocrine, musculoskeletal, hematological, neuropsychological, immune (allergies), and head, eyes, ears, nose, and throat. Historical and

current medical conditions including date of last menstrual period for female subjects will be recorded. History of tobacco and alcohol use (never, current, former) will also be collected.

Surgical history will include a review of all surgical procedures completed in the prior 5 years and any surgery completed at any time in the treatment area.

EFP history will include the start date of the condition and any family history of EFP.

8.2.2. Physical Examination

The complete physical examination should include evaluation of the head, eyes, ears, nose, throat, neck (including thyroid), cardiovascular system (including assessment of heart, peripheral pulses, presence or absence of edema), lungs, abdomen (including liver and spleen, bowel sounds), lymph nodes, musculoskeletal system (including spine, joints, muscles) neurological system (including cranial nerves, reflexes, sensation, strength), skin (excluding cellulite), extremities, and other conditions of note.

All examinations will be performed by a physician or health professional listed on the Form FDA 1572 and licensed to perform physical examinations. The investigator will review all physical exam findings for clinical significance. Any physical exam finding meeting the investigator's or sponsor's criteria for clinical significance will be recorded as an AE or SAE as appropriate.

8.2.3. Height and Weight

Height will be collected at screening only. Weight will be collected as outlined in the Schedule of Activities (Section 1.2). Any change from the Screening Visit in subject weight that is considered by the investigator to be clinically significant will be recorded as an AE (or SAE, if appropriate).

8.2.4. Fitzpatrick Skin Scale

The Fitzpatrick Skin Scale is a 6-level scale (Levels I-VI) for assessment of skin color and propensity for tanning. The skin types range from Level I: "Pale white skin, blue/hazel eyes, blond/red hair, always burns, does not tan" to Level VI: "Dark brown or black skin, never burns, always tans darkly". The investigator (or designee) will determine the Fitzpatrick Skin Type for all subjects at screening.

8.2.5. Vital Signs

Vital signs will be obtained at times outlined in the Schedule of Events and after the subject has been seated for 5 minutes (minimum) and will include systolic and diastolic blood pressures, pulse rate, respiratory rate, and body temperature. The results, date, and time for all vital sign assessments will be recorded.

On study treatment days (Days 1, 22, and 43), vital signs will be taken up to 4 hours prior to dosing and at 15 minutes and 30 minutes after dosing (body temperature is not required at the 15 minute postdose time point). The subject's vital signs must be stable, or repeated until stable before the subject can leave direct observation.

The investigator will review all vital sign values for clinical significance. Any vital sign value meeting the investigator's or sponsor's criteria for clinical significance will be recorded as an AE (or SAE, if appropriate).

8.2.6. *Electrocardiogram*

A 12-lead ECG recording will be conducted at the Screening Visit. The subject should be in a supine position for at least 5 minutes before the recording is conducted. Lead position will be that of a standard 12-lead ECG; no additional or special lead placements will be necessary. The ECG record should include a minimum of 5 heart cycles (beats).

If the ECG report shows QT prolongation with QTc \geq 450 ms, the investigator should repeat the ECG within 1 hour. If the initial findings are confirmed, the investigator should exclude the subject from study participation.

The investigator will review all other ECG results for clinical significance. Any ECG result meeting the investigator's criteria for clinical significance will be recorded as an AE (or SAE, if appropriate).

8.2.7. *Clinical Laboratory Determinations (Hematology, Chemistry, and Urinalysis)*

Clinical laboratory tests will be conducted according to the Schedule of Activities (Section 1.2). Required clinical laboratory tests are outlined in Section 10.2. Clinical laboratory tests will be performed by a designated central laboratory. The site will be provided with instructions for specimen collection, preparation, packaging and transport. The results of the tests will be returned to the investigational site.

Samples for laboratory testing may be collected under fasted or nonfasted conditions. Fasting early morning samples are preferred, but a random daytime sample is acceptable. The date and time of the sample collection must be documented on the laboratory report. Investigators must review and sign laboratory reports and document the clinical significance of each laboratory abnormality. New clinically significant laboratory abnormalities or clinically significant changes in laboratory values will be reported as AEs (or SAEs, if appropriate).

Clinical laboratory test data will be reviewed by the investigator, or designee, and additional clinical laboratory tests may be ordered at his/her discretion (eg, if the results of any clinical laboratory test falls outside the reference range or clinical symptoms necessitate additional testing to ensure safety). Any additional testing will be performed by the designated central laboratory (or local laboratory, if needed to ensure subject safety).

8.2.8. *Pregnancy Testing*

All female subjects of childbearing potential will have serum and/or urine pregnancy tests at the time points outlined in the Schedule of Activities (Section 1.2). Results must be available prior to protocol mandated study treatment and prior to MRIs. Subjects with positive results at the Screening Visit or on Day 1 will be ineligible for study entry. Any female subject that becomes pregnant during the study will be immediately withdrawn from the study and will have the pregnancy reported as per Section 8.3.5.

For all female subjects of childbearing potential, the subject's agreement to use contraception throughout their study participation (Screening Visit through Day 265, or for a minimum of

28 days after the last dose of study treatment for subjects who early terminate) will be documented.

8.2.9. Biopsy Follow-up Examination

The investigator will examine the biopsy site for evidence of ongoing AEs related to the biopsy and to determine if the biopsy site has healed at times specified in the Schedule of Activities (Section 1.2). The Day 85 and Day 265 Biopsy Follow-up Visits are not required for subjects who had less than 3 doses of study drug prior to 18 March 2020.

8.3. Adverse Events and Serious Adverse Events

The definitions of AEs and SAEs can be found in Section 10.3.

All AEs, including both observed or volunteered problems, complaints, signs or symptoms, and medically significant laboratory values must be recorded, regardless of whether associated with the use of study treatment. This would include AEs resulting from concurrent illness, reactions to concurrent medication use, or progression of disease states (excluding the disease under study). A condition present at baseline that worsens after initiation of study treatment will be captured as an AE; the onset date will be the date the event worsened. The AE should be recorded in standard medical terminology when possible.

8.3.1. Time Period and Frequency for Collecting AE and SAE Information

All SAEs and AEs will be collected by the investigator from the time of signing the informed consent through the Day 265 visit or for 28 days after the last study treatment for those who early terminate. For subjects who undergo the screening biopsy and are not subsequently dosed, AEs will be followed for 28 days after the biopsy. This will include any AEs that are ongoing at the time of completion/termination of the study. All ongoing AEs must be followed until resolution or for 28 days after the subject's last study treatment, whichever comes first.

All SAEs will be recorded and reported to the sponsor or designee within 24 hours, as indicated in Section 10.3. The investigator will submit any updated SAE data to the sponsor within 24 hours of it being available.

Investigators are not obligated to actively seek AEs and SAEs after conclusion of subject study participation. However, if the investigator learns of any SAE, including death, at any time after the subject has been discharged from the study, and the investigator considers the event to be reasonably related to the study treatment or study participation, including all medically significant and grade 4 labs, the investigator must promptly notify the sponsor.

The method of recording, evaluating, and assessing causality of AEs and SAEs and the procedures for completing and submitting SAE reports are provided in Section 10.3.

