^l Adverse events (AE)/serious adverse events (SAE) will be captured from time of informed consent signature until the Day 265 Visit or until 28 days after last dose of study drug whichever is later. There is no time limit on collection of SAEs considered to be related to study treatment.

Note: Unless otherwise stated above or outlined below (and with the exception of injection site reactions/local tolerability in the areas treated), all assessments should be completed prior to dosing on treatment days (Days 1, 22, and 43).

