Following a screening period of up to 35 days, qualified subjects will receive 0.84 mg of CCH per treatment area (each buttock or each thigh) for a total dose of 1.68 mg in both buttocks or both thighs per treatment session \times 3 treatment sessions (Day 1, Day 22, and Day 43). Buttock treated subjects will receive 0.84 mg of CCH administered as up to 12 injections (0.3 mL administered as three 0.1 mL aliquots per injection in each buttock). Thigh treated subjects will receive 0.84 mg of CCH administered as up to 12 injections (1.5 mL administered as five 0.3 mL aliquots per injection in each thigh).

Subjects will have MRI and (except as noted above) double punch biopsies of 3 selected target dimples 3 times during the study. All subjects will be followed for 265 days after the first dose of study treatment.

Subjects will participate in the study for approximately 305 days (10 months) plus any delays caused by the COVID-19 public health emergency. The duration of the study from first subject first visit to last subject last visit will be dependent upon the ability of the site to identify and enroll subjects. The entire study is expected to require about 24 months to complete.

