7.2. Subject Discontinuation/Withdrawal from the Study

Subjects may withdraw from the study at any time at their own request, or may be withdrawn at any time at the discretion of the investigator for safety, behavioral, compliance, or administrative reasons. The date of and reason for withdrawal from the study will be recorded.

If the subject withdraws consent for disclosure of future information, the sponsor may retain and continue to use any data collected before such withdrawal of consent. If a subject withdraws from the study, the subject may request destruction of any samples taken and not tested and the investigator must document this in the site study records.

Withdrawal from the study is required for any subject who becomes pregnant at any time during the study.

A subject may also be withdrawn from the study for the following medical or administrative reasons:

- Withdrawal by subject (reason must be specified).
- An AE.
- Death.
- A protocol violation (reason must be specified, for example: lack of compliance, use of a prohibited concomitant medication, etc).

- The subject was lost to follow-up.
- Other reasons (reason must be specified, for example: the subject moved, pregnancy, investigator decision, sponsor decision to terminate trial, etc).

If a subject discontinues from the study, all Early Termination procedures should be conducted as detailed in the Schedule of Activities. The date a subject discontinues and the reason for discontinuation will be recorded in the source documentation and the electronic case report form (eCRF). If, however, a subject withdraws consent, no additional procedures are required except the collection of AE information. This information should be recorded in the source documentation and the eCRF.

All subjects dosed prior to 18 March 2020 will be replaced. Subjects who receive their first dose of study drug after 18 March 2020 and subsequently withdraw from the study will not be replaced.

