10.3.4. Reporting Adverse Events and Serious Adverse Events

10.3.4.1. Reporting Adverse Events

Throughout the study, AEs will be documented on the source document and on the appropriate page of the eCRF whether or not considered treatment-related. This includes any new signs, symptoms, injury or illness, including increased severity of previously existing signs, symptoms, injury, or illness. Conditions existing prior to screening will be recorded as part of the subject's medical history. The investigator is responsible for assessing the relationship of AEs to the study medication; relationship will be classified as not related, unlikely related, possibly related, or probably related.

All AEs will be collected by the investigator from the time of signing the informed consent through the Day 265 Visit or for 28 days after the last study treatment in subjects who terminate early. All ongoing AEs must be followed until resolution or until the Day 265 Visit, or 28 days after the last dose of study medication for subjects who terminate early, whichever comes first.

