3.13. Safety Assessments

3.13.1. Adverse Events

Adverse events will be collected from the time of signing informed consent through the Day 265 Visit, or for 28 days after the last study treatment for subjects who terminate early.

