3.13.9. Follow-up Biopsy

The investigator will examine the biopsy site for evidence of ongoing AEs related to the biopsy and will determine if the biopsy site has healed. The follow-up biopsy examination will be conducted at the Day 1, Day 85 and Day 265 visits. The investigator will examine and confirm sufficient healing of the biopsy site before dosing on Day 1.

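### Non-serious biopsy adverse events that start after the last contact are not assured of being recorded for dosed women who leave between a post-treatment biopsy and its follow-up examination

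*Protocol*

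**What the plan says.** Three places tie an early terminator's AE collection to the last dose. Protocol 8.3.1 runs it "through the Day 265 visit or for 28 days after the last study treatment for those who early terminate". Protocol 10.3.4.1 has "through the Day 265 Visit or for 28 days after the last study treatment in subjects who terminate early". SAP 3.13.1 has "or for 28 days after the last study treatment for subjects who terminate early".

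Two places say something else. Footnote l of the Protocol Schedule of Activities runs collection "until the Day 265 Visit or until 28 days after last dose of study drug whichever is later", with no separate rule for women who leave early, and footnote k of SAP Table 2 repeats it. Protocol 7.2 keeps the collection of AE information going when consent is withdrawn but gives no end date.

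Only one rule counts from a biopsy, and it is for undosed women (Protocol 8.3.1): "For subjects who undergo the screening biopsy and are not subsequently dosed, AEs will be followed for 28 days after the biopsy".

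On examining the site, SAP 3.13.9 states: "The follow-up biopsy examination will be conducted at the Day 1, Day 85 and Day 265 visits". The Protocol schedule marks the same three visits and leaves the Day 251/Early Termination column blank in that row. For a woman who leaves, Protocol 7.2 says "all Early Termination procedures should be conducted as detailed in the Schedule of Activities".

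**The concern.** The trial takes a double punch biopsy at screening, at Day 71 (Dimple 2) and at Day 251 (Dimple 3). Protocol 2.3 lists infection and permanent scarring among the biopsy risks, and Protocol 9.1 justifies the small sample by the wish to limit exposure to this procedure. Yet for a dosed woman who leaves early, the clock for new AEs starts at the last injection, not at the last biopsy. She may leave before the examination meant to check healing, and the column she is directed to does not contain that examination.

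What is at stake is narrow: non-serious biopsy AEs, such as a minor infection or delayed healing, that start after the site last sees or speaks to her. In addition, the site has two collection rules that give different end dates for the same woman.

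**Working it through.** **Inputs**
- Third dose: Day 43 ± 3, so Day 40 to 46 (Protocol 1.2).
- Window for early terminators: last dose + 28 days (Protocol 8.3.1, 10.3.4.1; SAP 3.13.1).
- First post-treatment biopsy: Day 71 + 10, so Day 71 to 81 (first part of Protocol Table 1, and SAP Table 2). The continued part of Protocol Table 1 prints ±10, so Day 61 to 81. That may come from text extraction, so both are shown.
- Second post-treatment biopsy: Day 251 ± 15, so Day 236 to 266.
- Follow-up examinations: Day 85 ± 5 and Day 265 ± 5.

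**Check on the plan's own timeline.** SAP 3.1 gives 194 days of follow-up after Day 71: 265 − 71 = 194. It reproduces.

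**When the window closes.** Nominal: 43 + 28 = Day 71, the biopsy day itself. Range: 40 + 28 = 68 to 46 + 28 = 74.

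**Closing day minus day of the Day 71 biopsy**
- Biopsy on Day 71 to 81: from 68 − 81 = −13 to 74 − 71 = +3 days. Of the 7 × 11 = 77 whole-day combinations, 67 close before the biopsy, 4 on the same day and 6 after it.
- Biopsy on Day 61 to 81: from −13 to 74 − 61 = +13 days. Of the 7 × 21 = 147 combinations, 70 close before, 7 on the same day and 70 after.

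These counts show what the visit windows allow; they are not probabilities.

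**If dosing stopped early but she stayed for the biopsy.** With only the Day 1 dose, the window closes on 1 + 28 = Day 29. With the last dose on Day 22 ± 3, it closes on Day 47 to 53. For a biopsy on Day 71 to 81 that is between 71 − 53 = 18 and 81 − 29 = 52 days before it.

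**Day 85 examination.** It falls 85 − 71 = 14 days after the nominal close (range 80 − 74 = 6 to 90 − 68 = 22).

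**Day 251 biopsy.** The window closed 251 − 71 = 180 days earlier (range 236 − 74 = 162 to 266 − 68 = 198).

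**Difference between the two rules.** If footnote l is read as running to calendar Day 265, the end dates differ by 265 − 71 = 194 days for a woman whose last dose was on Day 43.

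**The case against.** The day counts are elapsed time, not lost data. The last-dose clause applies only once a woman has terminated early. While enrolled she is asked about AEs at every visit (Protocol 8.3.2), and that includes an attended Early Termination visit. At that visit the investigator also records local tolerability in the treated areas and rates the CR-PCSS and Hexsel scales on the standing subject. Dimples 2 and 3 lie within those areas. What is missing is a named check of healing, not all sight of the site. Protocol 7.1 encourages women who stop to complete the remaining visits. All of this stands, and it confines the gap to events that start after the last contact.

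A reader might infer that biopsy harm after Day 71 goes unrecorded altogether. The documents do not support this. Protocol 10.3.4.2 covers SAEs for 28 days after withdrawal for any reason, and 8.3.1 requires notification of later SAEs that the investigator learns of and relates to study participation.

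A reader might also infer that only SAEs are covered after withdrawal. Protocol 7.2 says otherwise, since AE information is still collected when consent is withdrawn. But it gives no end date, and 8.3.1 does not oblige investigators to seek AEs actively once participation ends. So 7.2 does not by itself assure collection.

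Finally, few women are exposed. The Day 71 biopsy applies to the 12 new women and to the 2 who had completed all three doses before the suspension, if willing: at most 14. A woman who leaves after attending Day 85 has had the Day 71 site examined.

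**Conclusion.** The point holds in limited form. For dosed women who leave between the Day 71 biopsy and Day 85, or between the Day 251 biopsy and Day 265, the plan does not assure that non-serious biopsy AEs starting after the last contact are recorded. The last-dose window closes from 13 days before to 3 days after the first of these biopsies (to 13 days after under the ±10 heading), and about 180 days before the second. These figures assume three doses given within their visit windows.

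The passages also disagree: three count from the last dose, two footnotes take the later of two dates, and 7.2 has no end date. The size of that disagreement rests on reading footnote l as calendar Day 265, because a woman who has left has no Day 265 Visit.

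It is tempting to conclude that AE incidence in the Safety Population will be understated. The documents give no withdrawal rate and no rate of late biopsy complications, so no such effect can be shown. A complication that causes a woman to leave comes before her departure, and 7.2 has the reason recorded. The point is worth acting on because the rule works badly for this group and is cheap to mend, not because a bias has been demonstrated.

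**What to change.** Reconcile Protocol 8.3.1, 10.3.4.1, 7.2 and footnote l with SAP 3.13.1 and footnote k of SAP Table 2, so that early terminators have one AE data-collection window. It should not close before or at the last biopsy, in keeping with the biopsy-based window that 8.3.1 already gives undosed women. As an illustration only, carrying over that 28-day rule would close collection on 71 + 28 = Day 99 (to 81 + 28 = Day 109) after the first post-treatment biopsy, past the Day 85 examination. After the second it would close on 251 + 28 = Day 279 (range Day 264 to 294). The length is for the sponsor to settle.

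Separately, reconcile the Early Termination column with Protocol 8.2.9 for women who leave with an unexamined biopsy site.

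The cost is wording in both documents and at most one contact for each affected woman.

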8.3.2. Method of Detecting AEs and SAEs

Care will be taken not to introduce bias when detecting AEs and SAEs. Open-ended and nonleading verbal questioning of the subject is the preferred method to inquire about AE occurrences.

At each visit, subjects will be queried regarding any AEs that have occurred since the last visit. Subjects will be asked to volunteer information concerning AEs with a nonleading question such as, "How do you feel?". Study site personnel will then record all pertinent information. The study drug compliance record should also be reviewed to detect potential intentional or unintentional overdoses.

8.3.3. Follow-up of AEs and SAEs

After the initial AE/SAE report, the investigator is required to proactively follow each subject at subsequent visits/contacts. All SAEs and nonserious AESIs will be followed to resolution, stabilization, the event is otherwise explained, or the subject is lost to follow-up. Further information on follow-up procedures is provided in Section 10.3.

